4. TRIAL DESIGN

General Design

A single-center randomized controlled trial to determine whether use of the Acumen™ HPI Software Feature to guide hemodynamic management in cardiac surgery post-CPB and up to 8-hours post-CPB reduces the mean duration of hypotension (defined as MAP < 65 mmHg). The results of the HPI arm will be compared with a control group (non-HPI arm). In the control group, the clinician will use non-protocolized standard of care management per clinician and provider judgement.

In accordance with 21 CFR 812.3(m), this trial does not meet the definition of a significant risk investigation for the following reasons:

- The devices in the treatment group are being studied in accordance with the indications for use and intended use granted by FDA, and therefore are not investigational devices;
- The devices in the treatment group are not implants;
- The devices in the treatment group do not present a potential for serious risk to the health, safety, or welfare of a subject as only subjects requiring an arterial line will be eligible for enrollment in the Trial;
- The devices in the treatment group are of substantial importance in diagnosing, mitigating, or treating disease, or otherwise preventing impairment of human health and Class II (general and special) controls provide a reasonable assurance of the safety and effectiveness of adjunctive predictive cardiovascular indicators;
- The Trial relies on the intervention of a learned intermediary prior to initiation of treatment, as the clinicians are utilizing their own clinical judgment in deciding appropriate treatment;
- The HPI Pressure & Flow Optimization Protocol provides recommendations for treatment. Clinicians are instructed to validate the appropriateness of protocol recommendations, and provide treatment based upon their clinical judgment;
- The devices in the treatment group are not of substantial importance in curing disease.

Subject participation will include preoperative trial eligibility screening and consent, planned surgical intervention, post-intervention follow-up through discharge, and 30 days post procedure. Discontinued subject data will be analyzed under intent-to-treat and data will be used for safety and performance analyses.

This trial will be conducted in a manner that is consistent with the applicable regulations and in accordance with current Good Clinical Practice (GCP).

Randomization and Blinding

Subjects will be randomized into two arms, the HPI arm and the non-HPI arm. The randomization will be done automatically by the Electronic Data Capture (EDC) system. The subject will be blinded. Due to the nature of the interventions, the investigators and treating anesthesiologist, anesthesia nurse, intensivist and critical care nurse will not be masked to group allocation.

The HPI arm will utilize the HemoSphere Advanced Monitoring Platform with the Acumen™ HPI Software Feature. The treating cardiac anesthesiologist/anesthesia nurse in the operating room and the critical care

THIS DOCUMENT CONTAINS CONFIDENTIAL AND PROPRIETARY INFORMATION OF EDWARDS LIFESCIENCES, LLC. IT MAY NOT BE REPRODUCED OR DISCLOSED WITHOUT PRIOR WRITTEN PERMISSION FROM EDWARDS LIFESCIENCES, LLC.

Edwards Lifesciences, Edwards, the stylized E logo, HemoSphere, Acumen IQ, Swan Ganz and ForeSight Elite are trademarks of Edwards Lifesciences Corporation.

nurses/intensivists/advance practice providers in the ICU will be trained to understand Acumen™ HPI Software Feature and the advanced hemodynamic parameters provided. The treating anesthesiologist, anesthesia nurse, intensivist, and critical care nurse will be provided with guidance by means of a flowchart suggesting what to treat and what the cause of hypotension is (see Figure 3. HPI Arm Protocol). Timing of treatment and choice of treatment is then left to the discretion of the attending intensivist and critical care nurse.

In the non-HPI arm, clinicians will be using non-protocolized standard of care to treat subjects.

[figure not shown]

Figure 3. HPI Arm Protocol

Note: Clinicians should validate the appropriateness of protocol recommendations, and provide treatment based upon their clinical judgment.

Schema

Screening and consenting subjects will occur during the pre-anesthesia visit. Once the subject is consented, the subject will undergo a Mini-Mental State Examination (MMSE).

After the subject has consented and prior to surgery, the subject will be randomized into the HPI arm or the non-HPI arm (control group). The randomization assignment must not be revealed to the clinicians until surgery. If a clinician randomizes the subject, they must not be involved in the care of the subject in the OR. A clinical research coordinator or a designee who is delegated to consent and/or randomize the

THIS DOCUMENT CONTAINS CONFIDENTIAL AND PROPRIETARY INFORMATION OF EDWARDS LIFESCIENCES, LLC. IT MAY NOT BE REPRODUCED OR DISCLOSED WITHOUT PRIOR WRITTEN PERMISSION FROM EDWARDS LIFESCIENCES, LLC.

Edwards Lifesciences, Edwards, the stylized E logo, HemoSphere, Acumen IQ, Swan Ganz and ForeSight Elite are trademarks of Edwards Lifesciences Corporation.

subjects, may be unblinded to the randomization assignment to set up the devices in the OR accordingly. However, the delegated coordinator/designee must not reveal the randomization assignment to clinician prior to start of the surgery.

A baseline Creatinine, NT pro-BNP and Troponin will be drawn on the day of procedure. Any fluids and vasoactive medications administered, intraoperative complications, and adverse events that occurred during the procedure will be collected.

After surgery on post-operation day 1 (or within 24 hours of extubation), any fluids and vasoactive medications, post-operative complications, and adverse events will be collected. Troponin will be drawn and an MMSE will be administered.

[figure not shown]
Before hospital discharge (generally post-operation day 2-7, but may vary), another MMSE will be administered. Troponin and NT pro-BNP will be drawn POD1, 2, 3. Creatinine will be drawn POD 1, 2, 3.

While the subject is in the ICU, an ICU-specific Confusion Assessment Method (CAM-ICU 7) will be administered twice daily. This assessment will be administered for up to 7 days post-operation in the ICU or until the subject is transferred to the hospital floor.

While the subject is located on the hospital floor, a Brief Confusion Assessment Method (bCAM) be administered twice daily. This assessment will be administered until post-operation day 7 or until hospital discharge (whichever comes first).

Additional information will be collected when the subject is discharged. A 30-day follow up will take place 30 days (± 15 days) post-operation, either by phone call or in-person. If the follow-up takes place in-person, an MMSE will be administered at that time.

Figure 4. Sample Timeline Diagram

THIS DOCUMENT CONTAINS CONFIDENTIAL AND PROPRIETARY INFORMATION OF EDWARDS LIFESCIENCES, LLC. IT MAY NOT BE REPRODUCED OR DISCLOSED WITHOUT PRIOR WRITTEN PERMISSION FROM EDWARDS LIFESCIENCES, LLC.
 Edwards Lifesciences, Edwards, the stylized E logo, HemoSphere, Acumen IQ, Swan Ganz and ForeSight Elite are trademarks of Edwards Lifesciences Corporation.

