3. TRIAL OBJECTIVE AND ENDPOINTS

Trial Objectives

The objective of the study is to determine whether the use of the Acumen™ HPI Feature Software to guide hemodynamic management in the cardiac operating room (OR) post-CPB and the cardiovascular intensive care unit (CVICU) reduces the mean duration of hypotension (defined as MAP < 65 mmHg) as compared with the control group. The study is being performed in this patient population to provide information that cannot be readily obtained through additional non-clinical assessments.

Trial Endpoints

The primary endpoint is the reduction in the mean duration of hypotension (defined as MAP < 65 mmHg) post-bypass to the first 8-hour ICU period as compared with the control group.

Time of hypotension will be calculated as the sum of the following:

- From at least within 10 minutes of administration of Protamine in the post-CPB period until skin closure in the cardiac operating room (OR Period)
- Within 60 minutes upon arrival to CVICU and through the first 8 hours in the cardiac intensive care unit (CVICU Period)

Excluding a period of 15 minutes prior and 15 minutes after tracheal extubation

The following secondary endpoints will be analyzed:

- Additional definitions of hypotension:
 - Time Weighted Average (TWA) of MAP < 65 mmHg in the OR Period (T1)
 - TWA of MAP < 65 mmHg in the CVICU Period (T2)
 - TWA of MAP < 65 mmHg in the CVICU Period, pre extubation (T3)
 - TWA of MAP < 65 mmHg in the CVICU Period, post extubation (T4)
 - Mean duration in minutes of MAP < 65 mmHg in the time periods of T1, T2, T3 and T4
 - Mean duration in minutes of MAP < 60 mmHg in the time periods of T1, T2, T3 and T4
 - Mean duration in minutes of MAP < 55 mmHg in the time periods of T1, T2, T3 and T4
 - Mean duration in minutes of MAP < 50 mmHg in the time periods of T1, T2, T3 and T4
- Clinical endpoints:
 - Acute kidney injury (AKI)⁷, as defined by the modified KDIGO criteria, stages 1, 2 and 3
 - Neurocognitive deficit, as evaluated by the MMSE, CAM-ICU 7, and bCAM assessments. [bCAM will be used for delirium screening for patients who are deemed ready for transfer to the floor per ICU attending team's assessment, even if they are physically in the ICU]
 - Periprocedural Myocardial injury, measured with high-sensitivity Troponin I and defined by a threshold of 70 times the upper reference limit⁶. or >1400 pg/ml

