On the day of the procedure, the subject will be randomized into the HPI arm or the non-HPI arm (control group). If the subject is randomized into the HPI arm, the clinician will receive trial research nurse support and will use the Acumen™ HPI Software Feature with the Acumen IQ Sensor to monitor the subject. The initiation of HPI in the CVICU will not start until 15-30 minutes after the HPI arm subject arrives in the CVICU. Once HPI is initiated in the CVICU, HPI-based interventions will be held for at least 5 minutes before extubation and will also be held for at least another 5 minutes after extubation.

All subjects, regardless of randomization, will be equipped with an Acumen IQ Sensor. If the subject is not randomized into the HPI arm, the clinician will use non-protocolized standard of care.

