8.3. Multiplicity Adjustment

The family-wise Type I error rate between the primary efficacy and safety endpoints will be controlled using a hierarchical gatekeeping method. If the primary efficacy endpoint is not passed, then the safety endpoints will not be tested either. If the primary endpoint is passed, then the secondary endpoints will be tested using a one-sided α at the same level as the primary endpoint.

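### Nothing keeps the post-operative MMSEs, the bCAM or the 30-day contact from staff who know the arm, so the neurocognitive endpoint and part of 30-day event elicitation carry avoidable assessor bias

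*Combined protocol and SAP*

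**What the plan says.** **Who knows the arm.** Protocol section 4, Randomization and Blinding, says of the subject: "The subject will be blinded". It then says that "the investigators and treating anesthesiologist, anesthesia nurse, intensivist and critical care nurse will not be masked to group allocation" and gives the nature of the interventions as the reason. Under Schema, a coordinator or designee who consents or randomises "may be unblinded to the randomization assignment to set up the devices in the OR accordingly". That person may not tell the clinician before surgery starts, and no restriction is stated after that. Section 6, Procedure, adds that in the HPI arm "the clinician will receive trial research nurse support", so the research nurse also knows the arm.

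**What is assessed later.** On post-operative day 1, or within 24 hours of extubation, "Troponin will be drawn and an MMSE will be administered". A further MMSE comes before discharge, and another at 30 days if that contact is in person. In the ICU, "an ICU-specific Confusion Assessment Method (CAM-ICU 7) will be administered twice daily"; on the floor the bCAM takes over, twice daily to day 7 or discharge. The 30-day contact is by phone or in person. No section names the assessor or caller or requires that they be unaware of the arm.

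**How the results are used.** Neurocognitive deficit, judged by MMSE, CAM-ICU 7 and bCAM, is a secondary endpoint (protocol sections 3 and 7; SAP 3.3 and 8.4.2). SAP 8.3 says that if the primary passes, "then the secondary endpoints will be tested using a one-sided α at the same level as the primary endpoint". SAP 8.4.2 describes only rates and their difference for the clinical endpoints. Serious events through 30 days form the primary safety endpoint. Protocol section 9 has the investigator or designee determine whether events occurred, partly by questioning at each visit.

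**The concern.** The stated reason for unmasking is sound for staff who respond to the HPI display. It does not extend to someone who scores an MMSE before discharge or telephones the subject at 30 days. Every research role the protocol names may know the arm, and nothing separates those roles from the later assessments.

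MMSE and CAM scoring, and the questioning that brings out adverse events, depend in part on the rater. A rater who knows the arm and expects HPI to help can shift the result without intending to. SAP 8.3 looks for benefit one-sided, which is the direction such an expectation would favour. The same applies to the safety comparison: SAP 8.2.1 allows a conclusion that HPI reduces complications and serious events.

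The subject is already blinded, so assessment unaware of the arm on both sides is within reach for most of these contacts. The plan does not use it.

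**Working it through.** No figure in the documents needs reproducing. The check sets the sections side by side and then illustrates the size.

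**Step 1: does the reason for unmasking reach these assessments?**

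| Item | Timing | Rater-dependent | Assessor stated as unaware of the arm |
|---|---|---|---|
| Primary endpoint (MAP from the monitor) | Post-bypass through first 8 CVICU hours | No | Not needed |
| CAM-ICU 7 | Twice daily in ICU, scheduled from post-operative day 1 | Yes | No |
| bCAM | Twice daily to day 7 or discharge | Yes | No |
| MMSE | Day 1 (or within 24 h of extubation), before discharge, 30 days if in person | Yes | No |
| 30-day contact | Day 30 ± 15 | Partly | No |
| Creatinine, troponin | Days 1 to 3 | No | Not needed |

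The HPI-guided period ends with the first 8 CVICU hours (protocol sections 1 and 3). The rater-dependent assessments ordinarily follow it, so the stated reason does not cover them. CAM-ICU 7 is a practical exception: it is done at the bedside, where the critical care nurse is unmasked.

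**Step 2: how large could the effect be?** The documents give no rate of neurocognitive deficit or delirium, so the rates and shifts below are assumptions.

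Inputs:
- 157 per arm (SAP 2.4.3).
- One-sided α of 0.025 (SAP 2.4.3), or 0.0154, the Pocock level in SAP 8.1.2 and 8.1.4. SAP 8.3 sets the secondary level equal to that of the primary, and either reading is possible.
- Assumed true rate p, equal in both arms, and an assumed spurious lowering d of the HPI-arm rate.

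Formulas: SE = √(2p(1−p)/n); false-positive rate = 1 − Φ(z − d/SE), with z = 1.960 for α = 0.025 and 2.160 for α = 0.0154.

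Worked case, p = 0.20: SE = √(2 × 0.20 × 0.80/157) = 0.0451.
- d = 0.02: d/SE = 0.443; 1 − Φ(1.517) = 6.5%; at 0.0154, 1 − Φ(1.717) = 4.3%.
- d = 0.03: d/SE = 0.665; 1 − Φ(1.295) = 9.8%; at 0.0154, 1 − Φ(1.495) = 6.7%.
- d = 0.05: d/SE = 1.108; 1 − Φ(0.852) = 19.7%; at 0.0154, 1 − Φ(1.052) = 14.6%.

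Range over assumed rates, 157 per arm, for shifts of 2 / 3 / 5 points:

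| Assumed rate | α = 0.025 | α = 0.0154 |
|---|---|---|
| 15% | 7.2 / 11.2 / 23.6% | 4.8 / 7.8 / 17.9% |
| 20% | 6.5 / 9.8 / 19.7% | 4.3 / 6.7 / 14.6% |
| 30% | 5.8 / 8.4 / 16.0% | 3.8 / 5.7 / 11.6% |

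With the enrolled 175 per arm and a 20% rate, the values are 6.8 / 10.4 / 21.5% at 0.025 and 4.5 / 7.2 / 16.1% at 0.0154.

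These are probabilities given that the primary has passed and that a formal test is done.

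**The case against.** Several points on the other side stand.

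- **Limited reach.** The primary endpoint is computed from downloaded monitor data. AKI and myocardial injury rest on laboratory values, and mortality needs no rater's judgement. A reader might infer that open assessment undermines the main result; the documents do not support that.
- **A safety check exists.** Protocol section 10 has an independent Medical Reviewer adjudicate all adverse events for seriousness, anticipation and relatedness, and serious events are defined largely by concrete outcomes. A reader might infer that the safety endpoint as a whole is unprotected, which goes too far. The check is partial: the protocol does not say that the reviewer is masked, and adjudication cannot recover events never elicited.
- **The test may not happen.** SAP 8.4.2 presents only rates and differences for this endpoint, and testing under SAP 8.3 requires the primary to pass. The percentages above are therefore not this trial's error rate. Bias would still distort a descriptive difference.
- **No single rate is defined.** The documents give no cut-off or rule for combining MMSE, CAM-ICU 7 and bCAM into one deficit rate, so the 20% is hypothetical.
- **Silence is not exposure.** Floor nurses are not on the unmasked list, and the site may already use separate assessors. The plan neither requires this nor makes it checkable.

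It could also be objected that the fix needs an extra person, because for an HPI-arm subject both the coordinator and the research nurse may know the arm. This does not defeat it: the protocol lets a designee randomise and set up devices, so one role can take all allocation-aware tasks and leave the other unaware. But the documents give roles and not headcount, so such a person may not be available for every subject.

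**Conclusion.** The point holds as a limited, avoidable weakness. The justification for unmasking ends with the first 8 CVICU hours, yet the plan allows anyone aware of the arm to do the post-operative MMSEs, the bCAM and the 30-day contact. What is exposed is one rater-dependent secondary endpoint and part of event elicitation at 30 days.

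The size is illustrative. For an assumed 20% rate and shifts of 2 to 5 points, the conditional false-positive rate would be roughly 6.5% to 19.7% at 0.025, or 4.3% to 14.6% at 0.0154. The calculation also treats the whole endpoint as shifted, although it combines several instruments. The documents give no evidence that such a shift will occur or how large it would be. No size was computed for the safety endpoint. This is a cheap improvement, not a flaw that threatens the trial's main conclusion.

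**What to change.** Add to protocol section 4 (Randomization and Blinding, and Schema):

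1. Within the existing research team, the person who randomises a subject, sets up the devices or gives HPI support does not do that subject's post-operative MMSEs or 30-day contact. For example, one role takes all allocation-aware tasks, and the other does the assessments without access to the allocation in the EDC.
2. The arm is kept out of the CVICU-to-floor hand-off and off the assessment forms, and floor bCAM raters are not told it.
3. Each MMSE, CAM-ICU 7, bCAM and 30-day form records whether the assessor knew the arm.
4. CAM-ICU 7, and bCAM done while the subject is still physically in the ICU, may stay unmasked and are reported as such.

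The cost is protocol and delegation-log wording, one added form item and some scheduling effort. Masking will be imperfect in the ICU. Where no unaware team member is available, the awareness record applies instead of adding staff.

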6. SCHEDULE OF EVENTS & PROCEDURES

Schedule of Events

Study Procedure / Exam	Subject Screening	Procedure	Day 1 Post-Op	Day 2-7 Post-Op	Discharge	30-Day Follow Up (±15 Days)
Obtain Informed Consent	X					
Perform Inclusion / Exclusion Evaluation	X					
Obtain Medical History / Subject Demographics ¹	X					
MMSE	X		X	X ²		X ³
Assign Subject ID		X				
Randomize Subject		X				
Enter Subject Data into Monitor		X				
Vital Signs		X				
NT pro-BNP		X	x	X ⁴		
Troponin		X	X	X ⁴		
Creatinine		X	X	X ⁵		
ABG Labs		X				
Basic Labs		X				
Monitoring Duration		X				
Data download from Monitor		X				
Obtain Fluid and Vasoactive Medication Administration Record ⁶		X	X			
CAM			X ⁷	X ⁸		
Complete eCRFs	X	X	X	X	X	X

¹ Medical History / Subject Demographics / Surgical and Clinician Demographics can be obtained prior to procedure, either at the screening visit or on the day of procedure.

² MMSE will likely take place between Day 2-7 Post-Op, but this may vary.

³ Only required for patients who will be returning to Wake Forest Baptist Medical Center for 30-day follow up

⁴ Troponin and NT Pro-BNP to be drawn on POD 1, 2 and 3

⁵ Creatinine to be collected on POD 1, 2 and 3

⁶ Can be collected via the hospital record system anytime on the day of procedure or thereafter.

⁷ CAM will be administered twice during post-op Day 1. While in the ICU, CAM-ICU 7 will be utilized. Once the subject is transferred to the hospital floor, bCAM will be utilized.

⁸ CAM will be administered twice per day until Day 7 Post-Op or until the subject is discharged (whichever occurs first). While in the ICU, CAM-ICU 7 will be utilized. Once the subject is transferred to the hospital floor, bCAM will be utilized.

THIS DOCUMENT CONTAINS CONFIDENTIAL AND PROPRIETARY INFORMATION OF EDWARDS LIFESCIENCES, LLC. IT MAY NOT BE REPRODUCED OR DISCLOSED WITHOUT PRIOR WRITTEN PERMISSION FROM EDWARDS LIFESCIENCES, LLC.

Edwards Lifesciences, Edwards, the stylized E logo, HemoSphere, Acumen IQ, Swan Ganz and ForeSight Elite are trademarks of Edwards Lifesciences Corporation.

HPI CARE Trial
Protocol #: 2020-19

Record Adverse Events, if applicable		X	X	X	X	X
30-day follow up / Mortality Determination						X

Procedure

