5.2. Analysis Windows

No analysis windows will be used for this study. If some visits are far outside of the time, then a sensitivity analysis that removes the out of window visits may be performed to assess the impact of the out of window visits.

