8.4.2. Clinical Endpoints

The following clinical endpoints will be analyzed. The clinical endpoints will be analyzed on the mITT population.

- Acute kidney injury (AKI), as defined by the modified KDIGO criteria, overall and by stage 1, 2 and 3
- Neurocognitive deficit, as evaluated by the MMSE, CAM-ICU 7, and bCAM assessments. [bCAM will be used for delirium screening for patients who are deemed ready for transfer to the floor per ICU attending team's assessment, even if they are physically in the ICU]
- Periprocedural Myocardial injury, measured with high-sensitivity Troponin I and defined by a threshold of 70 times the upper reference limit or >1400 pg/ml

For each of the clinical endpoints, the rate in each arm and the difference in the rates for the arms will be presented.

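### The second MMSE has no fixed day, the first may float with extubation, and CAM testing stops at discharge, so an arm difference in stay or extubation time can by itself shift the neurocognitive rates

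*Combined protocol and SAP*

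**What the plan says.** Neurocognitive deficit, evaluated by the MMSE, CAM-ICU 7 and bCAM, is a secondary clinical endpoint (protocol Section 3; SAP 3.3 and 8.4.2). The timing rules are these.

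- **First post-operative MMSE.** Protocol Section 4, Schema, places this visit "After surgery on post-operation day 1 (or within 24 hours of extubation"), and says of it: "Troponin will be drawn and an MMSE will be administered". The Schedule of Events in Section 6 shows Day 1 only.
- **Second post-operative MMSE.** The Schema says: "Before hospital discharge (generally post-operation day 2-7, but may vary), another MMSE will be administered". Footnote 2 of the Schedule of Events agrees: "MMSE will likely take place between Day 2-7 Post-Op, but this may vary". The mark is in the Day 2-7 column, and the separate Discharge column is blank for the MMSE.
- **CAM.** Footnote 8 of the Schedule of Events: "CAM will be administered twice per day until Day 7 Post-Op or until the subject is discharged (whichever occurs first"). The Schema has the same stopping rule for the bCAM on the floor: "This assessment will be administered until post-operation day 7 or until hospital discharge (whichever comes first").
- **Analysis.** SAP 5.2: "No analysis windows will be used for this study". Its next sentence allows, but does not require, a sensitivity analysis without visits far outside their time. SAP 8.4.2: "For each of the clinical endpoints, the rate in each arm and the difference in the rates for the arms will be presented". SAP 6.2 makes no imputation beyond the dates of safety events.

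Time to extubation and hospital stay are exploratory outcomes compared between arms (SAP 8.6). SAP 8.3 says secondary endpoints will be tested if the primary endpoint passes.

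**The concern.** Extubation and discharge both happen after randomisation, and the plan itself treats them as outcomes that the intervention might change. They also limit when the MMSE is done and how many CAM tests a subject has. Two arms with the same cognition day by day could then show different rates, because one was tested on different days or tested more often.

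The two instruments need not err in the same direction. A shorter stay means fewer CAM tests, hence fewer chances of a positive result. If it also brings the MMSE forward, and deficits resolve over the first week, more deficits are found. A real effect could be masked or a false one created, and a crude rate difference would not show which.

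The SAP offers no remedy. The sensitivity analysis in SAP 5.2 is optional, and with no target day for the second MMSE it is unclear what would count as out of time.

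**Working it through.** The documents give no rate, power or sample size for this endpoint, so there is no plan figure to reproduce. The values of p, q, h and the 40% below are assumptions, shown as ranges and identical in both arms, so any difference comes from the schedule alone.

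**1. CAM, constant risk.** Two tests per day from POD 1, ending at discharge on day d or at POD 7, give k = 2 × min(d, 7) tests, at most 14. With chance p of a positive at each test, independently, the ever-positive rate is 1 − (1 − p)^k. Discharge on POD 5 gives k = 10, and on POD 6 gives k = 12. At p = 1%: 1 − 0.99^10 = 9.6% and 1 − 0.99^12 = 11.4%.

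| p per test | POD 5 | POD 6 | Difference (points) |
|---|---|---|---|
| 0.5% | 4.9% | 5.8% | 0.9 |
| 1% | 9.6% | 11.4% | 1.8 |
| 2% | 18.3% | 21.5% | 3.2 |
| 5% | 40.1% | 46.0% | 5.8 (before rounding) |

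For scale, take 175 per group (SAP 8.1.4). At p = 1% the standard error of the difference is √[(0.096 × 0.904 + 0.114 × 0.886)/175] ≈ 3.3 points, so 1.8 points is about 0.55 of a standard error.

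**2. CAM, falling risk.** Let the per-test risk on day x be 5% × q^(x − 1), with two tests a day.

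- Risk falling 30% a day (q = 0.7): 24.59% against 25.85%, a difference of 1.3 points.
- Risk halving each day (q = 0.5): 17.90% against 18.15%, a difference of 0.3 points.
- Positives only on POD 1-3, at 5% per test: 26.5% in both arms, a difference of 0.
- Both stays beyond POD 7: 14 tests in each arm, a difference of 0.

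**3. Second MMSE.** Assume a 40% deficit rate on POD 1, falling with half-life h days: D(d) = 40% × 0.5^((d − 1)/h). Suppose one arm is tested on POD 5 and the other on POD 6.

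- h = 1: 2.5% against 1.25%, about 1.2 points.
- h = 2: 10.0% against 7.1%, 2.9 points.
- h = 4: 20.0% against 16.8%, 3.2 points.
- h = 8: 28.3% against 25.9%, 2.3 points.
- No change over time: 0.

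This requires the test day, and not only the discharge day, to differ between arms.

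**4. First MMSE.** Under the same curve, testing one arm 6 hours later gives D(1) − D(1.25) = 6.4, 3.3, 1.7 and 0.9 points for h = 1, 2, 4 and 8, and 0 if the deficit rate does not change.

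**5. With common timing.** If every subject is tested on the same days, both arms have the same test count and timing, and the difference is 0.0 points under every assumption above.

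**The case against.** Much of the case against a stronger claim stands.

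- A reader might infer that the second MMSE is timed by discharge, so that an arm going home a day sooner is tested a day earlier. The text makes discharge an upper limit, and the Discharge column is blank for the MMSE. A shift in test day is possible but does not follow.
- A reader might infer that the rates will be biased. No document says that the arms will differ in stay or extubation. Bias also requires CAM risk to continue, or the MMSE deficit rate to change, over the days concerned. Since the two instruments can err in opposite directions, no net bias is shown.
- A reader might say that unmasked staff decide discharge. Protocol Section 4 lists investigators, anaesthesia staff, intensivists and critical care nurses as unmasked. It does not say who decides discharge from the floor. The mechanism does not need unmasking.
- Constant, independent risk per test through POD 7 is a simplification that favours a larger effect, and gaps of several days in stay would exaggerate it further. The one-day contrast and the falling-risk results are the fairer guide.
- The ever-positive rate is a construct used here. The SAP defines no cut-off, time point or rule for combining the tests, which is a related but separate gap. SAP 8.4.2 presents rates and a difference without naming a test.

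What remains is that nothing in the plan keeps test timing or test count the same in both arms, and nothing in the analysis accounts for either.

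**Conclusion.** The point holds as a conditional one. If the arms differ in stay or extubation time, the secondary neurocognitive rates can differ through test timing or number of tests alone. Size and direction cannot be known from the documents. With an assumed constant 1% chance of a positive per test, a one-day difference in stay (POD 5 against POD 6) gives 9.6% against 11.4%. The gap is smaller if risk falls with time, and zero if first positives occur only while both arms are still being tested. The MMSE effect needs both a difference in test day and a deficit rate that changes by day. The primary endpoint is unaffected. This is a cheap improvement to a secondary endpoint that SAP 8.3 allows to be tested, and it does not show that the planned comparison is invalid.

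**What to change.** 1. In the protocol (Section 4, Schema, and Section 6, Schedule of Events with footnote 2), set the second MMSE on one common day for all subjects, for example POD 3, or before discharge if earlier. Name that score in SAP 8.4.2 as the one analysed.
2. Reconcile the timing of the first MMSE between the Schema (POD 1, or within 24 hours of extubation) and the Schedule of Events (Day 1).
3. In SAP 8.4.2, report the CAM rate over a common window, for example POD 1-3, alongside the POD 1-7 rate, and give the number of CAM tests per arm. The POD 1-7 rate need not be demoted: a shorter window misses delirium first seen later.

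The cost is wording in those places. No tests are added, and the CAM part uses assessments already scheduled. Two limits remain. Some subjects may not be testable on the fixed day. Those discharged before it are still tested earlier, so some dependence on stay persists.
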